1 INTRODUCTION

1.1 Background

A.3. Sub-Saharan Africa HIV mortality

In 2016 in South Africa approximately 154,000 PWH died.¹ Of these deaths, 110,000 have been characterized as excess mortality due to HIV (HIV associated deaths).^{2,3} Overall, HIV-associated deaths are associated advanced disease defined by a low CD4 count.⁴⁻⁶

A.4. In-Hospital and Post-Hospital Mortality in Africa

Inpatient mortality among people with HIV (PWH) in Africa is uniformly high ranging from 17.2 to 29.6% across the continent, including in South Africa.⁴⁻⁶ Following discharge from an index hospitalization the mortality is also high. In our preliminary work we have observed a 26% mortality in the 6 months after hospital discharge. This observation is consistent with mortality from other reports: 50% mortality at twelve months and 30% and 31% at six months reported from Tanzania, Kenya, and South Africa, respectively^{7,8}

A.5. The contribution of Post-Hospital Mortality to Overall Death among People with HIV

In South Africa there are approximately 84,633 public sector acute care hospital beds of which approximately 25% are adult medicine beds.⁹ By extrapolating the post-discharge mortality we observed to all discharges among PWH in South Africa we can estimate the annual mortality among PWH with a hospital discharge in the past six months. Considering the national proportion of all admissions that are for PWH, the average length of stay, and the annual readmission rate an estimated 240,000 PWH are admitted to medicine wards in South Africa annually.^{10,11,12,13} A six-month post-hospital mortality of 26% suggests a total of 62,374 post-hospital deaths among PWH. This number of deaths represents 40% of the approximately 154,000 total annual deaths among PWH in South Africa.^{1,2} A modest reduction in post-hospital deaths could substantially reduce overall HIV mortality in South Africa.

A.6. Causes of Post-Hospital Death

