1.2 Study objectives

The overarching goal of this proposal is to demonstrate clinical trial feasibility, acceptability, and preliminary efficacy of structured post-discharge medical home visits to reduce mortality following the transition from the hospital to home. We are proposing a pilot randomized clinical trial (RCT) to determine preliminary efficacy, feasibility of trial implementation and intervention delivery, acceptability of the intervention, the effect of the intervention on barriers to care, and to obtain detailed baseline psychosocial and medical needs to inform intervention refinement and explain outcomes (Figure 1).

The primary objectives of this study are:

1. To estimate 6 month mortality rates and assess for evidence of efficacy of the Home Link intervention compared to care as usual.
2. To determine the feasibility, acceptability, and effect of the Home Link intervention on identified barriers to care.
3. To characterize medical and behavioral needs among participants in the study.

The secondary objectives of this study are:

1. Determine post-hospital health care out-of-pocket costs for participants
2. Assess re-admission
3. Estimate 12 month mortality by study arm
4. To understand experiences around the time of the passing of the participant from the family members perspective

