Alcohol use	Alcohol use disorder identification test (AUDIT), shortened version	Baseline, 6 months	Proportion

Medical conditions and psychosocial needs will be assessed prior to hospital discharge and post-hospital by using Home Link visit and other care contact records.

a. Medical assessment prior to hospital discharge: Clinical data will be abstracted or specifically obtained for the study, if not in the clinical record: HIV viral load, CD4 count, HIV drug resistance testing, Xpert Ultra for rapid TB diagnosis, discharge diagnoses, and discharge medications.

Blood will be drawn from all participants living with HIV for drug resistance testing; however, we will only conduct the drug resistance test if the viral load result is >1000 copies/mL. We may use leftover specimen from the drug resistance test to repeat the viral load and drug resistance test using a plasma separation card in collaboration with the National Institute for Communicable Diseases (NICD).

b. Psychosocial assessment prior to hospital discharge: social support, depression, economic status, and HIV stigma will be measured. The 12-item HIV stigma scale⁴⁵ (including enacted, internalized, and anticipated stigma components), CES-D (short) depression scale, MOS social support instrument, food security, and AUDIT alcohol use instrument will be administered to participants prior to discharge (E002).

c. Post-hospital services delivered: All post-hospital assessments (Home Link visit clinical instrument (HL001), participant challenges identified during patient-centered counseling sessions (from structured counselor notes), triage decisions from the discharge officer, findings on laboratory testing, and clinical evaluation during inpatient or ambulatory care that Home Link arm participants receive will be abstracted from hospital or clinic paper or electronic records and

the electronic National Health Laboratory Service records. These data will be organized to describe the intensity of care, psychosocial needs, clinical decision making, and most common clinical scenarios.

Sampling: All participants will have in-hospital laboratory and psychosocial assessments. All participants in the Home Link arm will be included in the assessment of post-discharge needs and triage outcomes.

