2.8 Analysis

2.8.1.1 Effectiveness analysis

Table 6. Effectiveness outcomes

Primary outcome	Mortality at six months by arm	Test of proportions (chi-square)
Secondary outcomes	Mortality at 12 months	Test of proportions (chi-square)
	Time to any non-acute follow-up	Cox proportional hazards
	Number of outpatient follow-up care encounters	Test of medians (Wilcoxon rank sum)
	Number of nights in hospital post-initial discharge	Test of medians (Wilcoxon rank sum)
	Self-reported cost of care	Test of medians (Wilcoxon rank sum)

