3.2 Study sample size justification

We propose to recruit a sample of 240 participants randomized 1:1 into care as usual and Care Link arms. The participants will be blocked to include 30 HIV-uninfected adults and 90 people living with HIV per arm. The sample size has been determined to be feasible given time and budget limitations while still providing insight into the efficacy. Using the base rate of mortality from our preliminary study of 26% and an alpha of 0.05 and a sample size of 120 split 1:1 in care as usual and Home Link arms we have represented power versus intervention arm mortality, with sub-group analysis limited to PWH, in Table 11. We note that the primary goal is feasibility and acceptability. We are appropriately powered only for a substantial decrease in mortality from 26% to 10%.

Table 9. Power by varying effect size on reducing post-hospital mortality

alpha	power	N	N1	N2	delta	p1	p2
.05	.1589	180	90	90	-.06	.26	.2
.05	.2527	180	90	90	-.08	.26	.18
.05	.3764	180	90	90	-.1	.26	.16
.05	.5212	180	90	90	-.12	.26	.14
.05	.6704	180	90	90	-.14	.26	.12
.05	.803	180	90	90	-.16	.26	.1
.05	.9019	180	90	90	-.18	.26	.08

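### Six-month mortality is analysed by a chi-square alone: the between-arm estimate has no stated effect measure or interval, and pre-discharge CD4 and age go unused

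*Combined protocol and SAP*

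**What the plan says.** The first primary objective (section 1.2) is "To estimate 6 month mortality rates and assess for evidence of efficacy of the Home Link intervention compared to care as usual". The analysis meant to deliver it is one row, given in the same terms in Table 3 (section 2.7.3) and Table 6 (section 2.8.1.1): the outcome "Mortality at six months by arm", to be compared by a chi-square test of proportions. Neither table names a risk difference, risk ratio or odds ratio, a confidence interval, or a covariate.

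The plan holds baseline information that bears on death. Section 1.1 states that "HIV-associated deaths are associated advanced disease defined by a low CD4 count". The medical assessment before discharge (section 2.7.4.3, item a) covers "HIV viral load, CD4 count, HIV drug resistance testing, Xpert Ultra for rapid TB diagnosis", taken from the record or obtained for the study when the record lacks it. Age and sex are sent to the randomising team for every participant (section 2.4.2).

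Section 2.8.1.4 plans a logistic regression of post-hospital outcomes on in-hospital measures, with sex, age and arm fixed in advance. It belongs to the social and medical needs analysis, does not name mortality, and serves to refine the clinical instrument and algorithm.

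**The concern.** A chi-square returns a p-value. A pilot that is meant to lead to a full trial needs the size of the mortality difference and the range of values compatible with the data. By Table 9 the power is only 16% to 52% for reductions of 6 to 12 points, so a non-significant p-value would say little.

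A comparison that ignores known predictors of death is also less precise than it could be. If CD4 or age happens to differ between arms, nothing in the planned analysis corrects for it. With 90 per arm such differences are not rare. Both values are already in the data collection plan, so the remedy needs no extra visit, sample or participant.

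**Working it through.** **Inputs.** Control mortality and alpha come from section 3.2: "Using the base rate of mortality from our preliminary study of 26% and an alpha of 0.05". Sidedness is not stated; two-sided is assumed and reproduces the table. Group sizes are "30 HIV-uninfected adults and 90 people living with HIV per arm". Table 9 uses the 90 PWH per arm, and so do I. (The sentence before the table speaks of 120 split 1:1; that is a separate inconsistency.) No document gives the strength of association between CD4 or age and death, so it is assumed and varied.

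**1. Reproduce Table 9.** Two-sided test, pooled variance under the null, no continuity correction:

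power = Φ{[|p1 − p2| − 1.96·√(2·p̄(1−p̄)/n)] / √[(p1(1−p1) + p2(1−p2))/n]}

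For 26% versus 10% with n = 90:
- p̄ = 0.18, and √(2 × 0.18 × 0.82/90) = 0.0573
- 1.96 × 0.0573 = 0.1122
- unpooled SE = √[(0.1924 + 0.0900)/90] = 0.0560
- power = Φ[(0.16 − 0.1122)/0.0560] = Φ(0.852) = 0.803, as stated

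All seven rows reproduce within 0.002. The small gaps in the top rows are the second tail; with it added they match to four decimals.

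**2. The interval that the tables do not ask for.** Half-width = 1.96 × SE. This is ±11.0 points at 26% versus 10%, and ±11.8 points at 26% versus 16%, where power is 0.376.

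Illustration: 23/90 versus 13/90 deaths.
- Difference = −11.1 points
- Test: z = 0.1111/√(0.2 × 0.8 × 2/90) = 1.86, p = 0.062
- Wald SE = √(0.2556 × 0.7444/90 + 0.1444 × 0.8556/90) = 0.0590, so the 95% CI is −22.7 to +0.5

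The test alone reads as negative. The interval shows that a large benefit remains compatible with the data.

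**3. Gain from adjustment.** Simulated trials, 90 per arm, 26% versus 10%, two independent normal baseline covariates. The raw risk difference is compared with one standardised from a logistic model. Runs used 4,000 to 8,000 trials per setting; the 8,000-trial ratios are shown.

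| Assumed AUC | Variance ratio, adjusted/raw | Reduction, rounded over runs | CI half-width: 11.0 × √(1 − reduction) |
|---|---|---|---|
| 0.63-0.64 | 0.98 | 1-2% | 10.9 |
| 0.70 | 0.935 | 6% | 10.6 |
| 0.75 | 0.887 | 11% | 10.4 |
| 0.78 | 0.853 | 14% | 10.2 |

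The Monte Carlo SE of the ratio at AUC 0.70 is about 0.006. A separate 5,000-trial run gave reductions of 1.5%, 6%, 10% and 12.5% at AUC 0.64, 0.69, 0.73 and 0.76. With covariates unrelated to death, the loss was about 1 to 1.5%.

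**4. Power.** In simulations with one covariate (3,000 trials per setting), the move from chi-square to adjusted analysis gave:
- OR 1.5 per SD: 0.808 to 0.818
- OR 2.0 per SD: 0.815 to 0.844
- OR 2.5 per SD: 0.822 to 0.868
- OR 1.0 (useless covariate): 0.810 to 0.816

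That is about 1 to 5 points, of which roughly half a point comes from the form of the test rather than the covariate. The formula in step 1 with n/(1 − R²) per arm gives a similar scale: 0.803 at R² = 0, 0.843 at 0.10, 0.863 at 0.15. With no effect, the adjusted analysis rejected in 4.5% to 5.3% of trials.

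**5. Chance imbalance.** The SD of a standardised between-arm difference is √(2/90) = 0.149. The chance that it exceeds 0.2 SD is 2 × [1 − Φ(0.2/0.149)] = 18% per covariate. If the OR is 2 per SD (assumed; R² about 0.08), a 0.2 SD imbalance near 26% mortality shifts the raw difference by about 0.2 × ln 2 × 0.1924 × (1 − 0.08) = 2.5 points.

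**6. Room in the model.** Expected deaths in PWH are 90 × 0.26 + 90 × 0.10 = 23.4 + 9.0, about 32. That supports three terms, not a long list.

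**The case against.** The strongest reply is that an unadjusted comparison in a 1:1 randomised pilot is sound, and that the sponsor is candid about its limits: section 3.2 puts feasibility and acceptability first and says "We are appropriately powered only for a substantial decrease in mortality from 26% to 10" per cent. Objective 1 and the outcome's wording imply that mortality will be reported for each arm. This stands as far as it goes, but proportions by arm are not a between-arm estimate with an interval.

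The reply also says that the prognostic strength is unproven. Section 1.1 links low CD4 to HIV deaths in general, not to death after discharge, and no section says that age predicts death here. That stands: a gain near nil is within the plausible range.

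Four stronger readings are tempting and are not supported.
- A reader might infer a gain of 10% or more at AUC 0.70. The larger simulations give about 6%.
- A reader might call adjustment free. CD4 is timed before discharge, not before randomisation. Completion of the baseline laboratory assessment is itself a feasibility indicator (Table 4), so completeness is unknown. Dropping participants without CD4 could cancel a gain of this size.
- A reader might infer that section 2.8.1.4 creates a rival efficacy result. It does not: Table 6 assigns the primary test, and 2.8.1.4 states a different purpose.
- A reader might use the p = 0.062 example to argue for adjustment. The unadjusted interval also includes zero, so the example supports reporting an interval and nothing more.

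**Conclusion.** The point holds as a low-cost improvement, not as an error. The larger gap is that the between-arm estimate implied by objective 1 has no stated effect measure or interval. The smaller one is that CD4 and age are left out: about 1 to 14% of the variance of the risk difference over AUC 0.64 to 0.78, or a half-width of 10.9 to 10.2 points instead of 11.0, plus cover against a chance imbalance that could move the raw difference by a few points. These sizes rest on assumed prognostic strength, 90 PWH per arm with complete outcomes, and mortality of 26% and 10%. A reader might infer that the planned chi-square is biased or invalid; it is neither.

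**What to change.** In Tables 3 and 6, make the six-month result the risk difference with 95% CI, standardised from a logistic model fixed in advance:

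- **PWH (the population of Table 9):** arm, age and log CD4.
- **All 240:** arm, HIV status and age, with CD4 entered for PWH only.
- **Headline:** state beforehand which of the two populations it is, so that there is one primary estimate. Keep the chi-square as supportive.
- **CD4 timing:** use only values from the index admission, before discharge and before any home visit. Values on the laboratory form scheduled at 26 and 52 weeks (Table 10) must not enter.
- **Missing CD4:** keep these participants in the model, for example by single imputation blind to arm plus a missing indicator, so that none are dropped.

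The cost is a few sentences in the plan and slightly more analysis work, with no new visits, samples or participants. The downsides are the limit that about 32 expected deaths in PWH put on the number of terms, and a loss of about 1% in variance if CD4 and age turn out not to be prognostic.

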2.4.2 Randomization

The total sample size is 180 HIV-positive and 60 HIV-uninfected adults. There will be a total of four study arms comprising of two arms for HIV uninfected and two arms for PWH. We will

perform individual randomization blocked by HIV-status to enroll 30 HIV-uninfected adults per arm and 90 PWH per arm (Figure 2).

[figure not shown]

Figure 2: Randomization Study Arms for Home Link Intervention

1. Randomization of hospital patients for recruitment: On each participant recruiting day, a list of all medical ward patients will be generated, and each patient will then be randomly listed in order of planned recruitment. Patients will be approached at any time after admission if they are next on the list for recruitment until the enrolment target is reached for that day. A new list will be generated each day including only those patients admitted 2 days prior (or on Thursday, Friday and Saturday on Mondays).
2. Randomization to study arm: After informed consent and completion of baseline CRFs the participant will be randomized to care as usual or Home Link arm.

Randomization will be conducted immediately after eligibility criteria for the participant has been documented and informed consent has been signed. Participants will be randomized 1:1 to either the care as usual or the Home Link intervention arms using computer-generated random numbers, stratified by HIV-status.

A study staff member will SMS a dedicated study telephone number – staffed by someone not linked to any other aspect of the conduct of the study. Details of the eligible participant, including randomization group (1=living with HIV; 2=living without HIV), initials (first two letters of the first name and first two letters of the surname), age, and sex, will be sent via SMS to the randomizing team. A member of the randomizing team will then relay the allocation details (within 15 minutes) to the study staff member

who requested the randomization via SMS. Proof of randomization will be sent to the study staff member who will place the proof into the participants' study file.

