2.5.2 Home Link study arm

The Home Link intervention will be delivered by a **home visit team** including a primary care nurse and counselor trained in patient-centered counseling (Table 1). A rotating hospital-based doctor will be available for pre-home visit clinical file review and post-visit discussion, via cell phone, for decision making and input on patient care during a household visit. We have termed this individual a "**discharge officer**". The discharge officer will be a Tshepong clinician who is working in the hospital. Supporting Home Link is expected to take <30 minutes of the physician's time during the day. The team will also consult with a GCP-trained, PHRU research doctor based at Tshepong Hospital prior to household visits and for advice regarding referrals, discharge from home-based care, and other queries.

Table 1. Home Link intervention team key members

Team member	Training	Location of service	Role
Primary Care Nurse	Professional Nurse	Home visit team	Clinical assessment and management
Counselor	High school diploma	Home visit team	Patient-centered counseling & home needs assessment
Discharge officer	Medical doctor degree	Based at hospital	Clinical support (via cell phone)
PHRU research doctor	Medical doctor degree	Based at hospital	First point of contact for clinical support

The home care team will travel via car to the participant's house one week after discharge and every two weeks thereafter until completing 6 visits or the participant is discharged from the Home Link intervention based on the clinical assessments.

Home visits: Prior to team departure for a participant's home: the discharge officer and PHRU research doctor will review the participant's medical file, including retrieving laboratory results pending at the time of discharge or the prior home visit, and add any patient specific recommendations for assessments to the Patient Assessment Instrument (Appendix A) for the nurse to use at the household.

At the household, the team will use the Patient Assessment Instrument to document findings and guide decision making in the following areas:

Primarily provided by the primary care nurse

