2.7 Post-discharge follow-up

The primary outcome is mortality six months after hospital discharge. Secondary outcomes include mortality 12 months after hospital discharge, number of nights spent in a hospital,

number of ambulatory clinical encounters after the index hospitalization, and patient out-of-pocket costs for medical care. Outcomes will be assessed through scheduled contact and completion of a structured questionnaire with the participant or designated next of kin (either telephonic or in person if telephonic fails) at 8, 12, 26, and 52 weeks. Mortality will be further ascertained through a 26 and 52 week review of the Tshepong Hospital file (including the affiliated Klerksdorp hospital files) and matching of participant national identification numbers to the vital statistics register through consultation with the Department of Home Affairs. Repeat hospitalization will be ascertained using self-report / next of kin report and hospital records. Most subsequent hospitalizations can be expected to be at Tshepong Hospital due to the substantial distance to reach the next nearest hospital (>50 km to a lower level facility). In our prior experience we have observed rare use of alternative hospitals. Clinic visit data will be ascertained by self-report followed by verification through review of clinic paper or electronic (tier.net) records and National Health Laboratory Service electronic records (TrackCare).

Table 2. Scheduled visit windows

Visit name	Period	Primary goal
8 week follow-up	20 – 70 days	Maintain contact with participant
12 week follow-up	71-150 days	Assess care engagement, care satisfaction, mortality
26 week follow-up	151 – 245 days	Assess care engagement, , mortality; conduct psychosocial assessment
26 week hospital file review	>26 weeks post-hospital	Abstract care visits, re-admission, death
26 week Home Affairs vital status review	>26 weeks post-hospital	Match South African ID numbers
26 week care verification	>26 week post-hospital	Use electronic and paper files to verify self-reported clinic visits
52 week follow-up	365-455 days	Assess care engagement, mortality
52 week hospital file review	>365 days post-hospital	Abstract care visits, re-admission, death
52 week Home Affairs vital status review	>365 days post-hospital	Match South African ID numbers

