2.7.2 Mortality

Mortality will be ascertained via:

- (1) Telephonic contact with participant (alive) or next of kin, as provided by the participant, reporting a death
- (2) Review of the Tshepong Hospital paper file
- (3) South African Home Affairs vital statistics query using the participant national ID number

Mortality will be assessed after six months and again after twelve months.

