2.7.4 Acceptability & Feasibility

2.7.4.1 Feasibility of Home Link

The goal of this assessment is to evaluate the feasibility of implementing the Home Link intervention and of endpoint ascertainment for the clinical trial of Home Link implementation.

Specific feasibility considerations are:

- 1) The proportion of participants in the Home Link arm who receive each scheduled/expected Home Link home visits
- 2) Success of the study team to ascertain six month mortality

We will assess the trial feasibility based on the proportion of eligible individuals who enroll and the proportion of participants that we are able to collect full outcome data on. We will assess the feasibility of implementing the intervention on the following measures: the proportion of planned home visits that are completed, the proportion of home medical assessments completed, the proportion of home medication reconciliation completed, the proportion of participants who receive patient-centered counseling, and the proportion of participants with identified food insecurity who receive food supplementation/parcels at the first home visit. The proportions will be considered individually and with a composite score to be interpreted in the context of the efficacy results with a general threshold that substantially more than half of components expected to be completed need to be completed for the intervention to be considered feasible.

Success will be based on *a priori* targets of $\geq 90\%$ of planned home visits completed, successful follow-up of $\geq 75\%$ of participants, and vital status ascertainment of $>90\%$ of participants.

Table 4. Feasibility Indicators

Numerator	Denominator	Measure
-----------	-------------	---------

Number with first Home Link visit	Total in Home Link arm	Proportion
Number of completed Home Link visits	Number of planned/attempted Home Link visits	Proportion
Number of home medical assessments completed	Number of planned/attempted/completed Home Link visits	Proportion
Number of home medication reconciliation completed	Number of planned/attempted/completed Home Link visits	Proportion
Number of patient-centered counseling sessions completed	Number of planned/attempted/completed Home Link visits	Proportion
Number of participants who received food parcels	Number of Home Link participants with identified food insecurity pre-discharge	Proportion
Number of participants with 6 month vital status ascertainment	All study participants	Proportion

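### The primary six-month mortality analysis has no rule for participants of unknown vital status, although the protocol's own target tolerates just under 10% unknown

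*Combined protocol and SAP*

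**What the plan says.** Section 2.7 sets the endpoint: "The primary outcome is mortality six months after hospital discharge". Tables 3 (section 2.7.3) and 6 (section 2.8.1.1) give its only analysis, "Test of proportions (chi-square", by arm. The same test is listed for twelve months. Neither table mentions HIV status, although randomisation is stratified by it (sections 2.3 and 2.4.2).

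Section 2.7.2 lists three sources of vital status: telephone contact with the participant or next of kin, the Tshepong file, and a Home Affairs query on the national ID number. It adds: "Mortality will be assessed after six months and again after twelve months". Section 2.7.4.1 sets a success target of "vital status ascertainment of $>90\%$ of participants", and Table 4 reports ascertainment over all participants together, not by arm. Form T001 (Table 8) records loss to follow-up, but no analysis rule is attached to it.

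The documents contain no analysis-set definition, no exclusion, imputation or censoring rule for unknown status, and no sensitivity analysis. Cox regression is planned only for time to non-acute follow-up.

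**The concern.** A comparison of proportions needs a dead/alive status for everyone in it. When status is unknown, someone must decide whether to drop, impute or bound. If the rule is not written down, that decision is made after the data are seen, and at the tolerated level of unknowns it can settle the result.

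There are also reasons to think unknown status may not be a matter of chance:

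- Only the Home Link team visits homes, one week after discharge and "every two weeks thereafter until completing 6 visits", so the arms may be traced unequally.
- Section 1.1 (A.6) reports that missing a scheduled visit was associated with later death. That concerns clinic attendance, not study tracing, but it makes loss related to death plausible.
- The 26-week contact window in Table 2 opens at day 151. A participant last contacted alive before about day 182, with no later record, has no established six-month status.

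Estimating six-month mortality and looking for efficacy is the first primary objective in section 1.2.

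**Working it through.** **Inputs from the documents.** Section 3.2 gives the control mortality and alpha ("Using the base rate of mortality from our preliminary study of 26% and an alpha of 0.05") and the design effect ("We are appropriately powered only for a substantial decrease in mortality from 26% to 10" per cent). Section 2.4.2 gives the size: "enroll 30 HIV-uninfected adults per arm and 90 PWH per arm". The vital-status target is above 90% overall.

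**Assumptions, not in the documents.** The share unknown by arm (15% care-as-usual [CAU], 5% Home Link), mortality among the unknown (17% to 60%), and HIV-negative mortality (5%).

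**1. Reproduce Table 9.** Power = Φ[(d − 1.96·SE0)/SE1], 90 per arm, 26% versus 10%.
- d = 0.16 and pooled p = 0.18.
- SE0 = √(2×0.18×0.82/90) = 0.0573.
- SE1 = √[(0.26×0.74 + 0.10×0.90)/90] = 0.0560.
- Power = Φ(0.85) = 0.803, as stated. The other rows also reproduce.
- With 81 per arm (10% unknown, unrelated to death) power is 76.0%, with no bias.

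**2. Is 9 unknown of 90 PWH per arm within the target?** That is 18 people. If all 60 HIV-uninfected participants are ascertained, 18/240 = 7.5% are unknown and the target is met.

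**3. Fragility.** Known deaths: 0.26×81 ≈ 21 and 0.10×81 ≈ 8. Pearson chi-square, no continuity correction:

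| Handling of the 9 unknown per arm | CAU | Home Link | Difference | p |
|---|---|---|---|---|
| Dropped | 21/81 | 8/81 | 16.0 points | 0.008 |
| All coded alive | 21/90 | 8/90 | 14.4 points | 0.008 |
| CAU unknowns dead, Home Link alive | 30/90 | 8/90 | 24.4 points | 0.00006 |
| CAU unknowns alive, Home Link dead | 21/90 | 17/90 | 4.4 points | 0.47 |

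**4. Bias when the unknown share differs by arm.** Let p be true mortality, u the share unknown and m mortality among the unknown. Observed risk is (p − u·m)/(1 − u) if unknowns are dropped and p − u·m if they are coded alive. Take p = 26% in both arms (no true effect) and u = 15% CAU, 5% Home Link. Positive values count against Home Link; type I error is for 90 randomised per arm.

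| m | Dropped: bias (type I error) | Coded alive: bias (type I error) |
|---|---|---|
| 26% | 0 (5.0%) | +2.6 points (7.0%) |
| 40% | +1.7 points (5.7%) | +4.0 points (9.9%) |
| 50% | +3.0 points (7.2%) | +5.0 points (13.0%) |
| 60% | +4.2 points (9.7%) | +6.0 points (17.1%) |

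For example, at m = 40% with unknowns dropped: CAU (0.26 − 0.06)/0.85 = 23.5%, Home Link (0.26 − 0.02)/0.95 = 25.3%. Reversing the split reverses every sign. At 15%/5% with m = 17%, below the average, dropping gives 27.6% versus 26.5%, which is 1.1 points in favour of Home Link.

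**5. Would Kaplan-Meier remove the bias?** Censor the unknown alive at one last contact, and let a fraction f of known deaths precede it. With D = p − u·m, the risk is 1 − (1 − fD)·[1 − (1 − f)D/(1 − fD − u)]. Take f = 0.5:
- m = 40%: CAU 1 − 0.90×(1 − 0.10/0.75) = 22.0%; Home Link 1 − 0.88×(1 − 0.12/0.83) = 24.7%. Bias 2.7 points, against 1.7 for dropping.
- m = 52%: 20.0% versus 24.1%. Bias 4.1 points, against 3.2 for dropping.
- m = 17%: 25.9% in both arms to one decimal. Bias about 0.1 point, against 1.1 for dropping.

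So Kaplan-Meier helps when the lost have lower later mortality and does worse than dropping when they die more often.

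**6. Stratification.** With 26% mortality in PWH and 5% in HIV-negative participants, the overall risk is 0.75×0.26 + 0.25×0.05 = 0.2075. The unstratified variance term is 0.2075×0.7925 = 0.1644. The within-stratum term is 0.75×0.1924 + 0.25×0.0475 = 0.1562, a ratio of 0.95. The unstratified test then has type I error of about 2[1 − Φ(1.96/√0.95)] = 4.4%, so it is slightly conservative, and stratifying brings it nearer 5%.

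**The case against.** A reader might infer that the chi-square itself is the fault and that unequal tracing does bias the result against Home Link. The documents do not support that, for four reasons.

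- **The gap is the missing rule, not the test.** Imputation or bounds work with a comparison of proportions. With unknowns dropped, a 15%/5% split gives no bias if their mortality equals that of the known.
- **Unequal tracing is not shown.** Outcome contacts at 8, 12, 26 and 52 weeks are the same in both arms, with next of kin as an alternative and an in-person attempt if the telephone fails. The hospital file and Home Affairs checks cover both arms, and clinic and laboratory records can show that someone was alive. Six fortnightly home visits from week 1 end at about week 11, some 15 weeks before the endpoint. No document says how many participants lack an ID number.
- **The direction is conditional.** It follows from the assumed split and the assumed mortality among the unknown.
- **Kaplan-Meier is not a cure** (step 5), so replacing the primary analysis with it is not justified on these grounds.

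It is also fair to say that this is a pilot: section 3.2 puts feasibility and acceptability first, and ascertainment will be reported as a feasibility measure. Read strictly, 10% unknown overall would miss the target.

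All of this limits the claim but leaves the gap. The fragility in step 3 needs no assumption about tracing and fits within the target (step 2). Pooled ascertainment would not reveal an imbalance between arms.

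**Conclusion.** The point holds as a missing prespecification. The primary comparison uses fixed status, is unstratified, and says nothing about unknowns that the protocol itself expects. At about the tolerated level, and at the design effect, their placement spans 4.4 to 24.4 points and p=0.47 to p<0.001. This rests only on the document's figures and on 9 unknown per arm.

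Bias is possible rather than demonstrated. Coding unknowns alive understates mortality in an arm whenever any of them died, and it distorts the difference when that shortfall differs by arm. Dropping them distorts an arm's risk unless their mortality equals that of the known. Under the assumed 15%/5% split the distortion is 1.7-4.2 points (dropped) or 4.0-6.0 points (coded alive) for 40-60% mortality among the unknown, against a 16-point design effect. This should be settled before analysis. It does not invalidate the trial.

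**What to change.** In Tables 3 and 6, for both six and twelve months:

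1. Make the primary estimate the risk difference with 95% CI, stratified by HIV status, among participants of known status. Define known status as a death by the time point or evidence of being alive at or after it.
2. State that unknowns are not coded as alive.
3. Report ascertainment by arm and by source (contact or next of kin, hospital file, Home Affairs).
4. Prespecify best- and worst-case bounds for unknown status, as in step 3 of the working.
5. Add a Kaplan-Meier risk at day 182, censored at the last date known alive, as a sensitivity analysis (with the matching time point for twelve months). Keep it out of the primary role, because it assumes non-informative censoring and does not reduce the bias if the untraced die more often.

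The cost is a little more analysis work and a less clear-cut result if the bounds are wide. The sponsor must also confirm that post-discharge death and last-contact dates are captured on F001 and A001. Table 8 mentions a date only for in-hospital death or discharge, on D001.
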